## **B) OPERATIONAL DESIGN:**

### **1. Questionnaire:**

Detailed clinical history and thorough clinical examination were conducted to assess subject eligibility to participate in the study.

### **2. Laboratory investigation:**

**Blood sampling, plasma and PBMCs isolation:** Study participants will be asked to donate blood samples (10 ml) at the start (basal) and at the termination of the study (4 weeks). Blood will be collected into heparinized tubes, diluted with an equal volume of DPBS (no  $\text{Ca}^{++}/\text{Mg}^{++}$ ), and peripheral mononuclear cells (PMBC) will be isolated by a standard Ficoll-Hypaque density gradient centrifugation method within 2h. Part of the plasma will be aspirated and frozen for analysis of liver and kidney functions. The lymphocyte band will be aspirated from the gradient interface, washed once with PBS supplanted with 1 mM EDTA and 0.1% BSA to remove platelets and once with a complete medium (CM; RPMI medium supplemented with 10% fetal bovine serum, 100-U/ml penicillin, 100 mg/ml streptomycin and 50 mg/ml gentamicin.), counted and assessed for viability in a trypan blue dye (0.2% (v/v) in PBS), and prepared as subsequently described for the different assays.

**Liver and kidney functions:** AST (serum glutamic oxaloacetic transaminase or SGOT), ALT (serum glutamic-pyruvic transaminase or SGPT), uric acid, creatinine will be assessed in plasma.

**Degranulation assay for NK cell activity:** NK cell activity will be measured with degranulation assay as previously described by [name] et al. (23). Briefly, 100 µl of heparinated blood will be used to examine either unstimulated control (RPMI 1640 medium alone), stimulated (combination of Phorbol-12-myristate-13-acetate (PMA, 50 ng/ml, Sigma, St. Louis, MO, USA) and Ca2+ ionophore (Ionomycin, 250 ng/ml, Sigma, St. Louis, MO, USA), positive control (PMA/Ionomycin plus cytochalasin (5 µg/mL, Sigma, St. Louis, MO, USA), IgG isotypic staining negative control. For stimulation, samples will be incubated for 5 hours at 37°C under 5% (v/v) CO2 with FITC-labeled mouse anti-human CD-107a (clone H4A3, BD Bioscience, San Jose, CA, USA) plus monensin (GolgiStop, BD Bioscience, San Jose, CA, USA), which will be added to a final concentration of 6 µg/mL 1 hour after incubation. In the IgG isotypic staining negative control sample, incubation will be performed with mouse anti-human FITC-labeled IgG AB (clone G18-145, BD Bioscience, San Jose, CA, USA) instead of FITC-labeled mouse anti-human CD-107a (34). At the end of incubation, BD PharmLyse (BD Bioscience) will be used to lyse RBCs. White blood cells will be collected by centrifugation (300x g, 5 min), washed once, re-suspended in 100 µl staining buffer, and then stained by incubation with 5 µl of PE-labeled mouse anti-human CD56 AB clone R19-760 (NCAM-1, BD Bioscience) and 5 µl of PerCP-labeled mouse anti-human CD3 clone SK7 (BD Bioscience) for 15 minutes at 37°C. After staining, cells will be centrifuged (300x g, 5 min), washed once, and re-suspended in FACS buffer. BD FACS Calibur with CellQuest software will be used for analysis (BD Bioscience, San Jose, CA, USA).

**Cell culture and flow cytometry:** BEAS-2B cells (ATCC) will be grown on collagen-coated (5 g/cm^2) plates in bronchial epithelial growth medium using the BEGM Bullet kit (Lonza, Walkersville, MD), maintained at 37°C, 5% CO2, seeded in 6-well plates and grown until 90% confluent. Cells will then be incubated with either PBS (control) or Biobran/MGN-3 100 µg/ml (Daiwa Technologies, Japan) for

72h. After harvesting, cells were washed with PBS, permeablized/fixed by BD cytofix/cytoperm buffer as per manufacture instruction, washed, collected, re-suspended in 100  $\mu$ l of the first block solution with 10% rabbit serum for 30 min at room temperature. Cells will then incubated for 15 min at 37° C with 5  $\mu$ l of either fluorescent-labeled monoclonal anti retinoic acid-inducible gene-1 (RIG-1) PE (Biorbyt, San Francisco, USA), monoclonal rabbit anti humans melanoma differentiation-associated protein-5 (MDA5) AB, clone # 33H12L34 (catalog # 700360, ThermoFisher Scientific, Rockford, IL, USA), monoclonal rabbit Anti-humans Myxoma Resistance Protein-1 (MX1) AB (catalogue # orb228747) (Biorbyt, San Francisco, USA), monoclonal rabbit anti-humans anti-interferon-stimulated genes-15 (ISG15) AB (catalog # ab133346) (Abcam, Cambridge, MA, USA), or the IgG isotype matched control AB (negative control). For RIG-1, cells will be washed once in FACS buffer, collected by spinning, re-suspended in FACS buffer and analyzed. For MDA5, MX1, and ISG15, cells will be washed in permeablized/fixed BD cytofix/cytoperm buffer, spun down, re-suspended in staining buffer, and exposed to the second block in 10% goat serum for 30 min at room temperature. Cells were finally stained by incubating with phycoerythrin-conjugated goat anti-rabbit IgG secondary antibody (catalog # F0110) at 10  $\mu$ L/10^6 cells (R&D Systems, Minneapolis, MN, USA). FACS Calibur (BD Biosciences) and BD Cell Quest Software (BD Biosciences) will be used for the acquisition and analysis of the data. All cell culture and flow experiments were performed in triplicates.

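### As written, plasma for AST, ALT, uric acid and creatinine is taken after the blood is diluted 1:1 with buffer; uncorrected, the values would read at roughly 0.33 to 0.39 of true

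*Combined protocol and SAP*

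**What the plan says.** Section 2 (Laboratory investigation), under blood sampling, describes 10 ml of blood per participant at baseline and again at a second draw. The handling steps then appear in this order:

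1. "Blood will be collected into heparinized tubes, diluted with an equal volume of DPBS".
2. Mononuclear cells "will be isolated by a standard Ficoll-Hypaque density gradient centrifugation method within 2h".
3. "Part of the plasma will be aspirated and frozen for analysis of liver and kidney functions".
4. "The lymphocyte band will be aspirated from the gradient interface".

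The next paragraph of that section lists the tests: AST, ALT, "uric acid, creatinine will be assessed in plasma". No dilution factor, correction, haematocrit measurement or separate chemistry tube is mentioned there or elsewhere in the document.

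The NK degranulation assay, in the same section, is described differently: "100 µl of heparinated blood will be used to examine either unstimulated control" and the other assay conditions, with no mention of dilution.

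**The concern.** Plasma removal is placed between the gradient step and the harvest of the interface band. That is the point at which the layer above the Ficoll would be drawn off. If the blood loaded on the gradient is already half buffer, that layer is a mixture of plasma and DPBS. Buffer does not enter the cells, so all of it dilutes the plasma fraction, and the plasma is diluted more than twofold.

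The four tests are the only laboratory safety measures described. The section on risk to subjects calls the risk negligible, and this panel is the only biochemical check on that statement. Eligibility rests on history and examination ("Detailed clinical history and thorough clinical examination were conducted to assess subject eligibility"), so the baseline panel is also the only chemistry described that could show unrecognised liver or kidney impairment. Both uses need absolute values that can be set against a reference range. Section 3 (Statistical analysis) reports continuous variables as mean ± SD, so the published figures would carry the error too.

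**Working it through.** The plan gives no figure for the dilution effect, so there is nothing to reproduce. The check is a mass balance.

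**Inputs from the document:** 10 ml blood per draw; one volume of DPBS per volume of blood; no correction stated.

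**Assumed, not in the document:** haematocrit H from 0.35 to 0.50; buffer stays outside the cells; the analytes do not leave the cells during handling.

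**Formula.** A blood volume V contains plasma V(1 − H). Adding V of buffer makes the fluid outside the cells V(1 − H) + V = V(2 − H). The measured fraction of the true concentration is

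f = (1 − H) / (2 − H).

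For a 10 ml draw at H = 0.45, there are 5.5 ml of plasma in 15.5 ml of fluid, so f = 5.5/15.5 = 0.355.

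| H (assumed) | f | 1/f |
|---|---|---|
| 0.35 | 0.65/1.65 = 0.394 | 2.54 |
| 0.40 | 0.60/1.60 = 0.375 | 2.67 |
| 0.45 | 0.55/1.55 = 0.355 | 2.82 |
| 0.50 | 0.50/1.50 = 0.333 | 3.00 |

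A wider range of H, 0.30 to 0.55, gives f from 0.41 to 0.31.

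**Reading against a limit.** The column 1/f is the multiple of an upper limit that would read exactly at that limit: about 2.5 to 3. As an illustration at H = 0.45, a true ALT of 100 U/L would read 100 × 0.355 = 35.5.

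**Correction afterwards.** A factor of 2, the natural guess for a 1:1 dilution, would still leave values at 2 × 0.333 = 0.67 to 2 × 0.394 = 0.79 of true. A single factor of 2.67 (H = 0.40) would give 0.394/0.375 = 1.05 of true at H = 0.35 and 0.333/0.375 = 0.89 at H = 0.50. Each participant's haematocrit would be needed for an exact correction.

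**Effect on the planned tests.** A factor common to all values cancels from a t statistic. In simulated data (40 per group, means 25 and 28, SD 6), t = −1.851 and p = 0.068 both before and after multiplying every value by 0.375.

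The factor is not perfectly common, because haematocrit varies. With an assumed mean of 0.41 and SD of 0.04, f has a coefficient of variation of about 4%. Against a between-person variation of 6/25 = 24%, as in the simulated data, the total becomes √(0.24² + 0.04²) = 0.243. In the before-and-after comparison, a person's stable haematocrit scales both draws equally, so relative change is preserved.

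**The case against.** The strongest reply is that sentence order is the only evidence. The paragraph is a condensed methods text. It never says that the chemistry plasma is diluted, nor that results are reported without correction. The degranulation assay appears to use undiluted heparinised blood, and no other draw is described. Some blood may therefore be set aside before dilution, although the sampling paragraph does not say so, and plasma could be handled in the same way. This stands, and it makes the finding conditional. It does not remove the need for a change, because a laboratory following the text would freeze diluted plasma.

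Two further points also stand. The document ties these tests to no reference range, threshold, screening decision or objective. Safety is also followed through weekly home visits and telephone reports (section 3, Subjects).

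A reader might infer more than the document supports:

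- **That every value is known to read at one third.** This needs the written order to be the actual order, no correction, and a haematocrit of 0.50.
- **That the comparison between arms is invalid, or biased towards no effect.** A nearly common factor leaves the planned t-tests essentially unchanged.
- **That haematocrit adds large noise.** The ratio 0.394/0.333 = 1.18 compares the two ends of the assumed range; the typical added variation is about 4%.

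**Conclusion.** The point holds in conditional form. The written procedure takes plasma for the four tests after a 1:1 dilution and provides no means of correcting for it. If it is followed and results are reported uncorrected, values would be about 61% to 67% too low. Means in clinical units would be wrong, and an individual value up to about 2.5 to 3 times an upper reference limit could look normal.

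The size rests on the assumed haematocrit of 0.35 to 0.50 and on buffer staying outside the cells. The statement that the t-tests are largely unaffected rests on haematocrit being similar in the two arms and reasonably stable between the draws. The influenza-like illness and NK cell objectives are not touched. What is at risk is the use of the trial's only laboratory safety values in absolute terms.

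**What to change.** In section 2 (Laboratory investigation), under blood sampling, state that at both draws:

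1. the whole blood needed for the NK degranulation assay is set aside first;
2. a 1 to 2 ml undiluted aliquot of the 10 ml already drawn is centrifuged, and its neat plasma is frozen for AST, ALT, uric acid and creatinine;
3. only the remaining blood is diluted with DPBS for the Ficoll step.

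Spinning the whole tube before dilution is not a substitute, because it would conflict with the whole-blood NK assay.

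**Cost.** One short spin per draw and slightly less blood for cell isolation; no extra blood or visit. If the NK assay takes 100 µl for each of its four listed conditions (0.4 ml), then 10 − 0.4 − 2 = 7.6 ml to 10 − 0.4 − 1 = 8.6 ml remain for the gradient. The aliquot contains at most 1 × 0.50 = 0.5 ml to 2 × 0.65 = 1.3 ml of plasma over the assumed haematocrit range, so the laboratory should confirm that the chosen volume is enough for four tests.

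**If samples are already processed.** Parts of the document are in the past tense, so this may be the case. The sponsor should then confirm from laboratory records whether the plasma was neat. If it was diluted, absolute values should not be reported or compared with reference ranges.

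### The rabbit-serum first block conflicts with the anti-rabbit secondary used to read MDA5, MX1 and ISG15, and may add background of unknown size to three of the four objective 4 readouts

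*Combined protocol and SAP*

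**What the plan says.** All of this is in the combined protocol and SAP, section B) Operational design, 2. Laboratory investigation, under Cell culture and flow cytometry.

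- **First block.** After harvest, fixation and permeabilisation, cells are placed in a "first block solution with 10% rabbit serum for 30 min at room temperature". No wash is described between this block and the primary antibody.
- **Primaries.** Three of the four are rabbit antibodies: "monoclonal rabbit anti humans melanoma differentiation-associated protein-5 (MDA5) AB", "monoclonal rabbit Anti-humans Myxoma Resistance Protein-1 (MX1) AB" and "monoclonal rabbit anti-humans anti-interferon-stimulated genes-15 (ISG15) AB". The RIG-1 antibody carries PE directly.
- **RIG-1 readout.** There is no secondary: "For RIG-1, cells will be washed once in FACS buffer, collected by spinning, re-suspended in FACS buffer and analyzed".
- **The other three.** "For MDA5, MX1, and ISG15, cells will be washed in permeablized/fixed BD cytofix/cytoperm buffer", spun down, blocked a second time in 10% goat serum and then stained: "Cells were finally stained by incubating with phycoerythrin-conjugated goat anti-rabbit IgG secondary antibody".
- **Negative control.** An isotype-matched IgG is listed alongside the primaries. Its host species is not given. The plan does not say whether it goes through the secondary step, or whether its signal is subtracted or used only for gating.

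Specific objective 4 refers only to expression levels measured by flow cytometry. Neither that objective, the laboratory section nor section 3, Statistical analysis, says whether the result is mean fluorescence intensity, percent positive cells or a fold change.

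**The concern.** In an indirect stain, the labelled secondary identifies the primary by its species. Here the species it recognises is also the species of the blocking serum. Rabbit IgG left on the cells by the block can therefore take up the PE label together with the rabbit primary, and the cytometer cannot separate the two. The goat serum used later matches the species of the secondary, but it does not mask rabbit IgG already on the cells.

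At stake is the reading of MDA5, MX1 and ISG15 in PBS-treated and Biobran-treated cells. A background shared by both conditions pulls an uncorrected ratio toward 1. If measurement noise grows with total signal, it also makes a real increase harder to detect in an experiment run only in triplicate.

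**Working it through.** The plan gives no signal, background or effect figure for this assay, so there is no stated number to reproduce. The check has two parts.

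**1. Tracing the reagents**

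| Step | MDA5, MX1, ISG15 | RIG-1 |
|---|---|---|
| First block | 10% rabbit serum | 10% rabbit serum |
| Wash before primary | none stated | none stated |
| Primary | unlabelled rabbit monoclonal | PE-labelled |
| Wash after primary | yes | yes |
| Second block | 10% goat serum | none |
| Detection | PE goat anti-rabbit IgG | direct |

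The conflict arises only in the middle column. The wash after the primary should remove unbound rabbit IgG. Nothing in the plan shows that it removes rabbit IgG already bound to fixed, permeabilised cells.

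**2. What a background would do**

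Assumptions, none of them from the documents: the specific signal in PBS cells is 1, the true fold change is f, and an additive background b (in units of that specific signal) is the same in PBS and Biobran cells.

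- Observed fold, uncorrected: (f + b)/(1 + b)
- Observed difference: (f + b) − (1 + b) = f − 1, whatever b is
- Fold after subtracting a control that carries the same b: (f + b − b)/(1 + b − b) = f

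For f = 2:

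| b | Uncorrected fold | Difference | Corrected fold |
|---|---|---|---|
| 0.1 | 2.1/1.1 = 1.91 | 1 | 2 |
| 0.5 | 2.5/1.5 = 1.67 | 1 | 2 |
| 1 | 3/2 = 1.50 | 1 | 2 |
| 2 | 4/3 = 1.33 | 1 | 2 |
| 3 | 5/4 = 1.25 | 1 | 2 |

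**Precision.** Assume further a coefficient of variation of 15% on total signal, three independent values per condition and a two-sided t-test at 0.05. The common SD is 0.15 × √{[(1 + b)² + (2 + b)²]/2}, and the standardised difference is d = 1/SD. Power comes from the noncentral t distribution with 4 degrees of freedom and noncentrality d√(3/2).

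| b | d | Power |
|---|---|---|
| 0 | 4.22 | 0.96 |
| 0.1 | 3.98 | 0.95 |
| 0.5 | 3.23 | 0.84 |
| 1 | 2.61 | 0.67 |
| 2 | 1.89 | 0.42 |

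The loss therefore runs from negligible to large, and the documents do not say where in that range the assay lies. Percent positive cells cannot be worked through in this way, because it depends on a gate that the plan does not define.

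**The case against.** The strongest reply is that this is a risk and not a demonstrated loss. A wash does precede the secondary, so b may be small, and at b = 0.1 a 2-fold increase still reads 1.91. The background is common to both conditions, so a difference in fluorescence is unbiased. An isotype control is already listed and, if treated identically, restores the mean fold change. Any bias in an uncorrected ratio is toward no effect and would not create a false claim of upregulation.

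All of that stands, and it limits the size of the point. It does not remove it. Correction cannot be presumed when the plan states neither the readout nor the use of the control, and does not say that the control goes through the secondary step. Subtraction also cannot recover precision if noise rises with total signal.

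Two stronger readings are tempting. A reader might infer that the block is certainly stained and that the effect is therefore diluted; the documents give no staining data and do not support this. A reader might also infer that the method makes RIG-1 look more responsive than the other three. The plan compares each protein with its own PBS control and plans no comparison across proteins. Direct and indirect stains would differ in scale whichever serum was used.

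**Conclusion.** As written, the first block is incompatible with the secondary for MDA5, MX1 and ISG15 and creates an avoidable risk of background. Across assumed backgrounds of 0.1 to 3 times the control signal, a true 2-fold increase would read between 1.91 and 1.25 as an uncorrected fold change. It would not be biased as a difference, nor on average as a fold change corrected with an identically processed isotype control. These figures rest on an additive background that is equal in both conditions; the power figures rest also on the assumed 15% coefficient of variation. The actual background is unknown.

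Severity is low. The point is confined to three of the four proteins in the in vitro objective 4. RIG-1, the incidence and incidence density of influenza-like illness, and the NK degranulation assay, which uses directly labelled antibodies, are unaffected.

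**What to change.** In the Cell culture and flow cytometry paragraph:

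1. Replace the 10% rabbit serum in the first block with 10% goat serum for MDA5, MX1, ISG15 and their isotype control.
2. State the host species of the isotype control, and carry it through the same wash, second block and secondary as the three primaries.
3. Name the readout and report isotype-corrected values.

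The paragraph mixes past and future tense, so the assays may already have been run with rabbit serum. In that case item 3 still applies wherever an isotype control went through the secondary step, and the report should mention the possible loss of precision.

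A tube with the secondary alone is a useful optional check on what the block contributes. It should not replace the isotype control as the value to subtract, because it contains no primary-type antibody and so misses non-specific binding of that kind.

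The cost is a change to a serum the method already uses and a few added sentences, plus one tube per run if the optional check is adopted. No participant procedure or sample size changes.

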### **3. Statistical analysis:**

Fisher's Exact test and OpenEpi, version 3.01, was used for comparing the incidence rates and the incidence density rates between groups. Mean  $\pm$  standard deviation is used to express continuous variables. Shapiro-Wilks test was used to determine the normality of data distribution. Two-tailed Student's t-test was used to compare Biobran/MGN-3 and placebo groups. Paired t-test was used to examine treatment effects within groups (i.e., comparisons of post-treatment versus pre-treatment).  $P \leq 0.05$  was considered statistically significant. SPSS version 20 was used for computing statistical analyses values.

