### 3. Subjects:

Ninety apparently healthy older adults  $\geq 56$  years were originally recruited from the residents of Zagazig city visiting outpatient clinics at Zagazig University Hospitals. Only local residents were recruited so as to facilitate follow-up home visits and to reduce the dropout rate. Old age is associated with NK cell senescence. We recruited subjects  $\geq 56$  years of age in order to meet the WHO definition of old age in African nations (32). In addition, this age is close to public service retirement in Egyptian society, which is associated with significant social, mental, and psychological stress and therefore could be associated with significant decline in NK activity.

Males and females were randomly assigned into two groups (n=40/group) that received either placebo or Biobran/MGN-3 (500 mg/day for 3 months). Both the health care giver and the participants were blinded to the ingested supplement. Participants' health were monitored via weekly home visits and they were instructed to report any complaint or side effect by phone to the health care giver.

Diagnosis of ILI was made by documenting the incidence of acute respiratory illness with a measured temperature of  $\geq 38$  °C with cough (Fitzner et al., 2017). After diagnosis, the subject was helped to follow the proper health management

plan by the health care giver. During the study, all participants were required not to take any vitamins or medications during the study without consultation.

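### No analysis is specified for the liver and kidney values or for complaints, and the plan's general comparison of means is uninformative about one to three very extreme individual values

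*Combined protocol and SAP*

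**What the plan says.** Under Laboratory investigation, blood is drawn "at the start (basal) and at the termination of the study (4 weeks", and "Part of the plasma will be aspirated and frozen for analysis of liver and kidney functions". The assays are AST, ALT, uric acid and creatinine: "uric acid, creatinine will be assessed in plasma". Under Subjects, participants are visited weekly at home and "they were instructed to report any complaint or side effect by phone to the health care giver". The same section says the groups "received either placebo or Biobran/MGN-3 (500 mg/day for 3 months".

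The Statistical analysis section mentions neither the laboratory assays nor complaints. For continuous variables in general, mean with "standard deviation is used to express continuous variables". The between-group method is "Two-tailed Student's t-test was used to compare Biobran/MGN-3 and placebo groups", and "Paired t-test was used to examine treatment effects within groups". A Shapiro-Wilk check is listed without saying what follows if it fails. Fisher's exact test and OpenEpi are assigned to incidence rates and incidence density, which the Specific objectives define for influenza-like illness (ILI) only.

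No section sets a limit for an abnormal laboratory value or plans a listing, a shift table or a tabulation of complaints. None of the four specific objectives concerns safety.

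**The concern.** Liver or kidney harm in a trial of this size may well show as large changes in a few people and not as a small shift in everyone. A comparison of means is poorly suited to that pattern, because one very large value raises the arm's mean and inflates its SD together.

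If the general methods are applied to these assays, which is the only route the plan offers, the likely output is four non-significant p values. The Risk to subjects section already calls the risk negligible on the strength of earlier studies. The laboratory values and complaints are the trial's own follow-up evidence on that claim, so it matters whether the planned analysis can bear on it. The ILI and NK cell conclusions are not affected.

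**Working it through.** The plan gives no figure for safety to reproduce. Its one power calculation concerns NK cell activity.

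**Inputs.** Arm size n = 40 (Subjects); n = 45 is also used because 90 participants are to be enrolled (Sample size). Significance is at 0.05, and the tests are the two-sample and paired t-tests (Statistical analysis). The ALT and creatinine distributions used below are assumptions, because the documents give none.

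**Step 1: limit of the t statistic.** Let k of n participants in one arm have a value M above a common level, with everyone else at that level.

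- Difference in means: kM/n.
- Sum of squares in that arm: M²k(n − k)/n; in the other arm, 0.
- Pooled variance: M²k(n − k)/[2n(n − 1)].
- Squared standard error (× 2/n): M²k(n − k)/[n²(n − 1)].
- Hence t = √[k(n − 1)/(n − k)]. M cancels.

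With ordinary variation among the other participants, t tends to this value as M grows. The paired t-test on changes within the arm has the same limit, with n − 1 degrees of freedom in place of 2(n − 1).

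| k | limiting t, n = 40 | p two-sample, n = 40 | p paired, n = 40 | p two-sample, n = 45 | p paired, n = 45 |
|---|---|---|---|---|---|
| 1 | √(39/39) = 1.00 | 0.32 | 0.32 | 0.32 | 0.32 |
| 2 | √(78/38) = 1.43 | 0.16 | 0.16 | 0.16 | 0.16 |
| 3 | √(117/37) = 1.78 | 0.079 | 0.083 | 0.080 | 0.083 |
| 4 | √(156/36) = 2.08 | 0.041 | 0.044 | 0.041 | 0.044 |

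The boundary lies between three and four very extreme values. Three of 40 is 7.5% of an arm.

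**Step 2: illustration (assumed values).** Placebo ALT has mean 25 and SD 10. In the supplement arm 39 participants have mean 25 and SD 10, and one has 300.

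- Mean = (39 × 25 + 300)/40 = 31.9.
- Sum of squares = 38 × 10² + (39/40) × 275² = 77,534; SD = √(77,534/39) = 44.6.
- t = 6.875/√[(44.6² + 10²)/40] = 0.95, p = 0.34.
- With 400 in place of 300, p = 0.33.

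**Step 3: less extreme values.** In 20,000 simulated trials per case (n = 40, assumed ALT mean 25 and SD 8), one participant in one arm was given a raised value. The share of trials with p ≤ 0.05 was 2.7% at ALT 120, 0.2% at 200 and none at 400. With three such participants it was 19.3%, 14.3% and 2.7%. For one participant with creatinine 3 (assumed mean 0.9, SD 0.2) it was 2.9%. Significance becomes less likely as the values become more extreme.

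**Step 4: would a test on counts do better?** No. Fisher's exact test gives p = 1.00 for 1/40 against 0/40, 0.24 for 3 against 0, 0.055 for 5 against 0, and 0.026 for 6 against 0. The gain comes from reporting individuals and intervals, not from another significance test.

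**Step 5: what zero events would show.** The exact two-sided 95% upper limit is 1 − 0.025^(1/n): 8.8% for n = 40 and 7.9% for n = 45.

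**Step 6: time covered.** The only follow-up sample is placed at 4 weeks and also at study termination, while supplementation lasts 3 months, about 13 weeks (3/12 × 52). Taken at the stated time, the sample leaves about 9 weeks of intake without a laboratory value.

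**The case against.** A reader might infer that the plan has chosen the t-test as its safety analysis, and that a serious individual signal would be reported as no difference. The documents do not support that.

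- The Statistical analysis section never names the laboratory values, and no section labels them as safety data. The t-test reaches them only as the general method for continuous variables. The gap is an unspecified analysis, not a stated wrong one.
- No section says that safety will be concluded from p > 0.05. The statement that risk is negligible rests on earlier studies.
- Nothing excludes looking at individual results. In the illustration the required summary would show 31.9 ± 44.6 against 25 ± 10, which an attentive reader would notice. The Shapiro-Wilk test rejected normality in every simulated case with 40 per arm.
- It would also be too strong to say that a marked rise can never give p ≤ 0.05. Four extreme values reach 0.041, and moderate ones occasionally cross by chance.

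All of this stands, and it limits how strongly the point can be put. It does not supply the missing analysis. Noticing a large SD is not a planned review, the normality check has no stated consequence, and the paired t-test also compares means. The pilot label, which the Sample size section gives to the ILI component, is a reason to keep the remedy small.

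**Conclusion.** The point holds as a gap in the analysis plan. Laboratory values and complaints are collected with no method named for either, and the general methods available are uninformative about a few extreme individuals. With 40 to 45 per arm, one, two or three very extreme values give limiting p values of about 0.32, 0.16 and 0.08 under both t-tests. These limits do not depend on the assumed ALT or creatinine distributions; the illustration and simulations do.

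The documents do not show that a signal would be concealed or that safety would be claimed from a non-significant test. They support a narrower conclusion: such a result would say little about individual liver or kidney abnormality, and the plan should say so. As written, any laboratory statement also covers only the first 4 weeks.

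**What to change.** In the Statistical analysis section, keep means and SDs of the laboratory values as description and add:

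- For AST, ALT, uric acid and creatinine separately, the number by arm of participants who move from within to above the laboratory's reference range, and a listing of each participant's change from baseline. With one follow-up sample there is a single change per person.
- The number of participants by arm with any complaint or side effect.
- Exact 95% confidence intervals for these counts, with the denominator stated. The 8.8% and 7.9% limits assume that all 40 or 45 are evaluable; missing samples, or baseline values already above the range, would raise them.
- A sentence that p > 0.05 on the means is not evidence of safety.

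Reconcile the 4-week sample under Laboratory investigation with the 3 months of supplementation under Subjects. Until then, limit the laboratory statement to the period that the sample covers.

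The cost is some wording and two extra tables. The laboratory table uses data already planned. The complaint table may also need a simple recording form, since none is described. The safety statement becomes less favourable, because an upper limit of about 8% to 9% is reported even with no events.
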